## **9.5 Changes to concomitant medications, treatments/ procedures**

Changes in concomitant treatments after Visit 0 are not allowed unless needed for the proper medical care and treatment of the subject for a specific medical condition.

After the subject is enrolled into the study, the Investigator must instruct the subject to notify the study site about:

- Any new medications
- Alterations in dose or dose schedules for current medications,
- Any medical procedure or hospitalization that occurred or is planned
- Any non-drug therapies (including blood transfusions).

The Investigator must document this information in the subject's case history source documents.

The use of spectacles and contact lenses (excluding refraction corrective contact lens for orthokeratology) is permitted. However, concomitant application of other ways of correcting refraction, possibly affecting evaluation of the investigational lens, is prohibited during the study. For example, laser in situ keratomileusis, PRK and refraction corrective contact lens (orthokeratology).

[figure not shown]
## **10 STUDY PROCEDURES AND ASSESSMENTS**

Below examinations and observations are carried out at Visit 0/0A, Visit 00/00A, Visit 1/1A, Visit 2/2A and Visit 3/3A. The same instruments and methods should be used for all measurements at all visits. Examinations and observations are outlined in tabular format in Section 6 of this protocol. Both the examination and the observation may be performed on the same day if the day is within the window for the examination and observation of the eye concerned (first or second operated eye). Also examination and observation can be performed separately over days if these are performed within the set window.

### **10.1 Description of Study Procedures and Assessments**

#### **10.1.1 Preoperative Examination (Visit 0/0A)**

- Informed consent  
Routine test conducted for cataract subjects is performed. Subjects still qualifies after these tests are explained this study. Ensure that the subject has read, understood, and signed and dated a statement of informed consent prior to undergoing any study specific testing. Even though routine test was operated before informed consent, these data can be use as study data.
- Demographics  
Confirm sex , age and race/ethnicity.
- Medical history  
Confirm systemic and ophthalmologic complication, ophthalmologic surgical history.
- Concomitant medications  
Indicate the concomitant medications used by the subject at the time of the examination.
- Urine pregnancy test (female subjects only)  
Perform a urine pregnancy test if the subject is female and of childbearing potential.
- Inclusion/exclusion criteria  
Ensure that the subject meets inclusion/exclusion criteria and meet all qualifications for participation.
- Visual acuity

- Manifest refraction  
Measure using an automated refractometer, and then perform a manifest refraction using the 100% contrast chart at 5m, under photopic lighting condition (100-180 cd/m^2).
- Slit lamp examination  
Record the presence or absence of clinically significant ophthalmologic findings.
- Dilated fundus examination  
Record the presence or absence of clinically significant ophthalmologic findings.
- Keratometry  
Keratometry will be performed using an automated keratometer.
- Target residual refractive error  
Indicate the amount of postoperative refractive error ( $\pm$ ) anticipated based on the power calculation software used for the lens power that is chosen. The target for all eyes shall be emmetropia (based on the distance focus power).
- Calculation by a new Alcon Toric calculator that incorporates ocular trends in Toric IOL planning  
Calculate the IOL model by a new Alcon Toric calculator that incorporates ocular trends in Toric IOL planning. The formula should be the Holladay Total SIA formula. Record the Anticipated Residual Refractive Astigmatism and Indicated IOL Alignment.
- Topography

Corneal topography should be measured and indicate whether the astigmatism is regular or irregular. Irregular astigmatism is an exclusion criterion and these subjects should not be enrolled in the study.

- Axial length  
Obtain the axial length by A-mode or IOL master.
- Anterior chamber depth (ACD)  
The ACD should be measured from the apex of the cornea to the anterior surface of the natural crystalline lens with A-mode or IOL master.
- Intraocular pressure  
Perform tonometry using a contact or a non-contact ocular tonometer.
- Adverse events, Device deficiencies  
Presence/absence of adverse events and device deficiencies are recorded since informed consent.

### **10.1.2 Surgery Day (Visit 00/00A)**

Record surgical information at Visit 00/00A. If subjects wish to be implanted into both eyes with TFNT20, obtain consent in continuation of the study from each subject prior to the surgery on the 2nd eye.

- Operative eye  
Indicate which eye is being implanted.
- Exclusion criteria during surgery  
Assess qualification according to the inclusion/exclusion criteria during the surgery. The incision site for this study is defined as temporal ( $\pm 15^\circ$ , or approximately 1 mm, for the horizontal meridian (OS:  $0^\circ$ , OD:  $180^\circ$ )).
- Final incision size  
Indicate final incision size (mm) to the nearest 0.1 mm.
- Problems during surgery

Indicate what problems, if any, occurred during surgery. If any exclusion criteria occur, discontinue the subject from the clinical study.

[figure not shown]
- Other procedures at this surgery  
Any other procedures performed at this surgery should be indicated. Since other procedures at this surgery are included in the exclusion criteria, discontinue the subject from the clinical study.
- Lens information  
Provide the IOL information (IOL model, refractive power, serial No.) also in the event of discontinuation of implant. Attach the adhesive label contained in the package of the investigational lens to the Study Participants Card.
- IOL axis orientation (dilated)  
Record the orientation (in degrees; 0 ~180 degrees) of the investigational lens axis (designated by indentations on the IOL optic). [REDACTED]  
[REDACTED]
- Medical history  
Confirm systemic and ophthalmologic complication, ophthalmologic surgical history.
- Concomitant medications  
Indicate the concomitant ocular medications used during the surgery.
- IOL observation  
Observe the IOL surface and the inside of the haptic and optic of the investigational lens with a slit-lamp microscope, and record the presence/absence of visible abnormal findings (debris on IOL surface, forceps marks on IOL surface, IOL discoloration, IOL opacities, IOL scratch, membrane generated on IOL, pigmentation on IOL, surface haze, other.). And regarding the observed findings, evaluate the clinical significance. If the problem may negatively affect postoperative visual acuity, etc., handle it as the clinical significant, and if possible, take photos.
- Adverse events, Device deficiencies  
Presence/absence of adverse events and device deficiencies are recorded since informed consent.
- Secondary surgical intervention

Record the presence/absence of any postoperative surgical procedure that may be caused by the investigational lens. The SSI include iridotomy/ iridectomy for pupillary block, vitrectomy for pupillary block, adjustment of the position of the investigational lens, removal of the investigational lens due to inflammation, exchange of the investigational lens, etc., but not limited to them. Meanwhile, retinal reattachment surgery and posterior capsule resection are not included as SSI.

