**Figure .7-1 Study Design**

## **7.2 Rationale for Study Design**

The purpose of this clinical study is to evaluate effectiveness and safety of the TFNT20 when implanted to replace the natural lens following cataract removal in at least one eye based on a new Alcon Toric calculator that incorporates ocular trends in Toric IOL planning.

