## 8 STUDY POPULATION

The study population includes approximately 30 subjects to be enrolled at 1 site.

To participate in the clinical trial, subjects must be  $\geq 20$  years of age with cataract who would be eligible to receive a TFNT20 lens in at least one eye based on a new Alcon Toric calculator that incorporates ocular trends in Toric IOL planning. Subject with no ocular pathology that could confound study outcome, must require clear cornea cataract extraction, and must desire an IOL that provides the potential for near, intermediate and distance vision and corrects astigmatism. Additional entry criteria are listed below in Sections 8.1 through 8.3.

Check all entry criteria at baseline (Visit 0/0A) and at both surgical visits (Visit 00/00A).

If the implantation was aborted and the IOL did **not** touch the eye, then the subject is required to discontinue from the study and standard of care for IOL implantation is followed. Refer to Section 10.3 Discontinued Subjects for further details. If the implantation was aborted and the IOL did touch the eye, then the subject is followed for safety evaluation on this eye only.

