### 8.1 Inclusion Criteria

Written informed consent must be obtained before any study specific assessment is performed. Upon signing informed consent, the subject is considered enrolled in the study.

Subjects eligible for inclusion in this study must fulfill **all** of the following criteria: Among the criteria listed below, ocular criteria relates to the study eye only.

1. Adults, 20 years of age or older at the time of informed consent for participating in this study, of either gender, Japanese patient diagnosed with age-related cataract.
2. Planned routine cataract surgery (need determined by the expert opinion of the investigator).
3. Eligible to be implanted with the TFNT20 as determined by a new Alcon Toric calculator in at least one eye that incorporates ocular trends in surgical planning.
4. To qualify for fellow eye implant with TFNT20, subject must have no clinically significant findings at the Visit 1 examination of the first implanted eye.

Note: This criterion only applies to subjects who are eligible for both eyes and wishes to be implanted into fellow eye with TFNT20.

5. Willing and able to complete all required postoperative visits.
6. Subjects for able to comprehend and sign the informed consent form for participating in this study.  
For the subjects who are eligible for both eyes and wishes to be implanted into fellow eye with TFNT20, subject has to comprehend and sign the informed consent form for the second eye surgery and the study examinations prior to the examinations at Visit 0A.
7. Clear intraocular media other than cataract.
8. Subjects for whom postoperative emmetropia is planned (spherical equivalent  $\pm$  0.50 D).
9. Potential postoperative BCDVA of 0.5 decimal or better.

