## **8.2 Exclusion Criteria Prior to Cataract Surgery**

Subjects fulfilling **any** of the following criteria are not eligible for participation in this study. Among the criteria listed below, ocular criteria relates to the study eye only.

1. Any disease or pathology, other than cataract, that (in the expert opinion of the investigator) is expected to reduce the postoperative BCDVA to a level worse than 0.5 decimal
2. Prior retinal detachment.
3. Irregular corneal astigmatism as assessed by topographer per investigator decision.
4. Pregnancy or lactation, current or planned, during the course of the study.
5. Participation in another concurrent clinical trial.
6. Pupil less than 6mm after dilation.
7. History of anterior segment (corneal, anterior chamber, sulcus) or posterior segment (uveal, vitreo-retinal) pathology including retinal vascular occlusive disease, retinal detachment or peripheral retinal laser photocoagulation, ARMD, glaucoma

(uncontrolled or controlled with medication) or ocular hypertension, diabetic retinopathy, retinitis pigmentosa and any optic nerve pathology.

8. History of previous intraocular or corneal (refractive or trauma related) surgery.
9. Any other planned ocular surgical procedures including but not limited to LRI/Astigmatic Keratotomy and LASIK
10. Subjects with conditions that increase the risk of zonular rupture during cataract extraction procedure that may affect the postoperative centration or tilt of the IOL.
11. Presence or history of any condition or finding that makes the subject unsuitable as a candidate for cataract surgery or study participation or may confound the outcome of the study, in the opinion of the Investigator.

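### An event at second-eye surgery discontinues the whole subject, so the Day 30-60 refraction of an already implanted first eye is not assured, although the analysis is per eye

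*Protocol*

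**What the plan says.** **Stopping is by subject.** Protocol Section 10.1.2 is headed for Visit 00/00A, so it governs both the first and the second operation. For problems during surgery it says "If any exclusion criteria occur, discontinue the subject from the clinical study". For additional procedures it says "Since other procedures at this surgery are included in the exclusion criteria, discontinue the subject from the clinical study". Section 8 discontinues the subject when implantation is aborted before the lens touches the eye. After an abort with lens contact it says "If the implantation was aborted and the IOL did touch the eye, then the subject is followed for safety evaluation on this eye only".

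**Preoperative eligibility is by eye.** Section 8.2, like 8.1, states "Among the criteria listed below, ocular criteria relates to the study eye only". Section 8.3, which lists the intraoperative exclusions, has no such sentence and speaks of the patient.

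**Analysis is by eye.** The primary endpoint is a percentage of eyes. Protocol Section 12.2 and SAP Sections 2.1 and 2.2 define the AAS, the Best-Case Analysis Set (BAS) and the safety set as sets of eyes. Protocol Section 12.4.1.2 and SAP Section 4.3 use both eyes of a bilateral subject. SAP Table 4-1 runs the primary test on the AAS with observed data only, and Protocol Section 12.5 rules out imputation.

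**Timing of the second eye.** Under Section 8.1, "subject must have no clinically significant findings at the Visit 1 examination of the first implanted eye", and the subject must "sign the informed consent form for the second eye surgery and the study examinations prior to the examinations at Visit 0A". Section 8 adds a recheck of the entry criteria at each surgery.

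**The concern.** The rule that ends participation and the sets that define the analysis use different units. In a bilateral subject, an intraoperative event in the second eye can stop the subject while the first eye, implanted without incident, still awaits its primary measurement. Nothing about the first eye has changed, yet its Visit 3 refraction is no longer assured.

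The AAS still includes that eye, because its implantation succeeded. Without a Visit 3 refraction it would leave the numerator and the denominator of the primary test. Its remaining scheduled safety visits could also be missed, although the safety set includes it. The loss would come from wording and could be avoided.

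**Working it through.** **1. Can second-eye surgery come before the first eye's Visit 3?** Table 3-1 places Visit 1 at Day 1-2 and Visit 3 at Day 30-60. The stated conditions for the second eye are the first eye's Visit 1 findings, consent, the Visit 0A examinations and the criteria recheck. None of them refers to Visit 2 or Visit 3 of the first eye. From the end of the Visit 1 window to the start of the Visit 3 window there are 30 - 2 = 28 days in which the second operation could fall. Figure 7-1 is not shown and might set a longer interval. If it puts the second surgery after the first eye's Visit 3, this loss does not arise.

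**2. What is collected after discontinuation?**
- Section 10.2: at an unscheduled visit where the subject discontinues, exit procedures follow Table 3-1 and Section 10.1, as far as possible.
- Section 10.3.2: examinations at discontinuation are done if the investigator judges them necessary. If a lens remains in place, the subject is told of the need for safety follow-up at 30-60 days and asked to cooperate.

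A Visit 3 refraction is therefore possible, but no text requires one.

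**3. The plan's own power figure.** Inputs from Protocol Section 12.8: n = 30 eyes, null rate 0.292, assumed rate 0.609, one-sided alpha 0.025, exact binomial test. The critical value r is the smallest r with P(X ≥ r | n, 0.292) ≤ 0.025.
- For n = 30, r = 15, with exact alpha 0.0131.
- Power = P(X ≥ 15 | 30, 0.609) = 91.9%, close to the stated 91.6%. The figure is not in dispute.

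**4. Expected loss of first eyes.** The documents give no bilateral share, no rate of intraoperative exclusion and no interval between surgeries. Assumptions: 30 subjects, B of them bilateral (5 to 15, so 35 to 45 eyes), an event at a proportion q of second surgeries (3% to 5%), every second surgery before the first eye's Visit 3, and no refraction obtained after an event.

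Expected first eyes lost = B × q. Chance of losing at least one = 1 - (1 - q)^B.

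| B | q | Expected lost | Share of eyes | P(at least one) |
|---|---|---|---|---|
| 5 | 0.03 | 0.15 | 0.15/35 = 0.4% | 1 - 0.97^5 = 14% |
| 15 | 0.05 | 0.75 | 0.75/45 = 1.7% | 1 - 0.95^15 = 54% |

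With B = 0, which is the configuration used in Section 12.8 (30 eyes from 30 subjects), the loss is zero.

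**5. Effect on power** (same exact test, eyes treated as independent).

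| Eyes | r | Power |
|---|---|---|
| 30 | 15 | 91.9% |
| 32 | 16 | 92.4% |
| 33 | 16 | 94.8% |
| 34 | 16 | 96.5% |
| 35 | 17 | 95.1% |
| 44 | 20 | 98.7% |
| 45 | 20 | 99.1% |

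Power is at least 92.4% for every n from 32 to 45. It does not rise steadily with n because r moves in whole eyes, so the order of 34 and 35 carries no meaning here.

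**The case against.** **Existing follow-up may be enough.** Section 10.3.2 names 30-60 days, which is the Visit 3 window, and exit procedures under Section 10.2 would include a manifest refraction. This stands in part: a reader might infer that the first eye's data are certain to be lost, and the documents do not support that. But the 30-60 day follow-up is a request made for safety, and exit procedures at an unscheduled visit need not fall in the window. The measurement is not assured.

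**The second surgery may be late.** Figure 7-1 could space the operations. This cannot be excluded, and it limits how firmly the point can be put.

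**Eyes with an intraoperative exclusion.** A reader might infer that an eye in which implantation was completed despite a Section 8.3 criterion, such as a non-temporal incision, is wrongly lost from the primary test in the same way. The documents do not settle this. The eye appears to fit the AAS, because the safety-set definition contrasts successful with aborted implantation. But Protocol Section 12.4.1.2 and SAP Section 4.3 confine the analysis to eligible eyes, so it may leave as ineligible. Collecting its refraction under an unchanged AAS could bring excluded eyes into the test. It is therefore not counted in the loss above.

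**Section 8.3 stops nobody.** Correct: it lists criteria. The instructions to discontinue are in Sections 8 and 10.1.2.

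**Abort after lens contact.** Section 8's specific rule can stand beside the general one in 10.1.2, so this is not a firm contradiction. The wording still has two readings: follow-up limited to that eye, or only that eye limited to safety follow-up. The first would drop the fellow eye.

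**Conclusion.** The point holds as a minor gap between subject-level discontinuation and per-eye analysis. It concerns a successfully implanted first eye whose subject is discontinued because of an event at second-eye surgery. Under the stated assumptions the average loss is 0.15 to 0.75 eyes, or 0.4% to 1.7% of eyes. These rates are assumed, not taken from the documents, and the loss is zero if all subjects are unilateral or if the surgeries are spaced beyond Visit 3.

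Two stronger conclusions are not supported. The trial is not left underpowered: the calculated power at every eye count from 32 to 45 exceeds that at the planned 30. Nor is a biased result shown. Section 9.3 makes the first eye the one with the smaller anticipated residual astigmatism (with a tie-break on cataract), so lost first eyes would not be a random draw. Nothing in the documents, however, says how first eyes fare in subjects who have an event at the second surgery, so no direction can be given.

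**What to change.** Reconcile Protocol Sections 8, 10.1.2 and 10.3.2 with the per-eye analysis sets:

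- State that discontinuation because of an event in one eye does not by itself end the already scheduled Visit 2 and Visit 3 data collection, subject to consent, on a previously and successfully implanted fellow eye.
- State which of the two meanings of the Section 8 sentence on abort after lens contact is intended.
- For an eye that meets a Section 8.3 criterion but in which implantation was completed, reconcile Section 10.1.2 with the safety set. Also reconcile the restriction to eligible eyes (Protocol 12.4.1.2, SAP 4.3) with the AAS named in SAP Table 4-1, so that its status in the primary test is explicit. It should not be assumed to enter that test.

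Section 11.5 already separates participation from analysis in this way: a subject who becomes pregnant is not discontinued, and her data leave only the BAS.

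For the fellow eye the cost is protocol wording, with no visits beyond those scheduled and no change to the analysis sets. The third item also needs a matching clarification in the SAP. No surgical or clinical management rule is proposed.

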### **10.1.3 Postoperative Examinations (Visit 1/1A, Visit 2/2A and Visit 3/3A)**

Below examination and observation are carried out at Visit 1/1A, Visit 2/2A and Visit 3/3A.

- Visual acuity (Visit 1/1A, Visit 2/2A and Visit 3/3A)

- Manifest refraction (Visit 1/1A, Visit 2/2A and Visit 3/3A)  
Measure using an automated refractometer, and then perform a manifest refraction using the 100% contrast chart at 5m, under photopic lighting condition (100-180 cd/m^2).
- Slit lamp examination (Visit 1/1A, Visit 2/2A and Visit 3/3A)  
Record the presence or absence of clinically significant ophthalmologic findings.
- Dilated fundus examination (Visit 3/3A)  
Record the presence or absence of clinically significant ophthalmologic findings.
- Keratometry (Visit 1/1A and Visit 2/2A (if needed). Visit 3/3A.)  
Keratometry will be performed using an automated keratometer.
- Topography (Visit 1/1A and Visit 2/2A (if needed). Visit 3/3A.)

Corneal topography should be measured and indicate whether the astigmatism is regular or irregular.

- Axial length (Visit 1/1A and Visit 2/2A (if needed). Visit 3/3A.)  
Obtain the axial length by A-mode or IOL master.
- Anterior chamber depth (ACD) (Visit 1/1A and Visit 2/2A (if needed). Visit 3/3A.)  
The ACD should be measured from the apex of the cornea to the anterior surface of the natural crystalline lens with A-mode or IOL master.
- Intraocular pressure (Visit 1/1A, Visit 2/2A and Visit 3/3A)  
Perform tonometry using a contact or a non-contact ocular tonometer.

- Posterior Capsule Opacification (Visit 1/1A, Visit 2/2A and Visit 3/3A)  
Indicate the presence/absence of PCO. If PCO is present, it will be graded as clinically non-significant, clinically significant or clinically significant requiring YAG as follows:
  1. *Clinically Non-significant*: Early development of PCO, including fibrosis and proliferation of lens epithelial cells, observable by slit-lamp biomicroscopy. Causes no apparent decrease in VA subjectively (e.g., glare) or objectively (e.g., decrease in visual acuity).
  2. *Clinically Significant*: Increased PCO with early subjective and objective VA changes but does not require posterior capsulotomy.
  3. *Clinically Significant Requiring YAG*: Clinically significant PCO adversely affecting subject's VA and requiring posterior capsulotomy.
- Posterior capsulotomy (Visit 1/1A, Visit 2/2A and Visit 3/3A)  
Indicate whether a posterior capsulotomy was performed or not. If it was performed, report the date of the procedure and size.
- IOL observation (Visit 1/1A, Visit 2/2A and Visit 3/3A)  
Observe the IOL surface and the inside of the haptic and optic of the investigational lens with a slit-lamp microscope, and record the presence/absence of visible abnormal

findings (debris on IOL surface, forceps marks on IOL surface, IOL discoloration, IOL opacities, IOL scratch, membrane generated on IOL, pigmentation on IOL, surface haze, other.). And regarding the observed findings, evaluate the clinical significance. If the problem may negatively affect postoperative visual acuity, etc., handle it as the clinical significant, and if possible, take photos.

- IOL position change (Visit 1/1A, Visit 2/2A and Visit 3/3A)  
Tilt and/or decentration should be reported if greater than 10 degrees or 0.5mm.
- Adverse events, Device deficiencies (Visit 1/1A, Visit 2/2A and Visit 3/3A)  
Presence/absence of adverse events and device deficiencies are recorded since informed consent.
- Secondary surgical intervention (Visit 1/1A, Visit 2/2A and Visit 3/3A)  
Record the presence/absence of any postoperative surgical procedure that may be caused by the investigational lens. The SSI include iridotomy/ iridectomy for pupillary block, vitrectomy for pupillary block, adjustment of the position of the investigational lens, removal of the investigational lens due to inflammation, exchange of the investigational lens, etc., but not limited to them. Meanwhile, retinal reattachment surgery and posterior capsule resection are not included as SSI.

